1.3 Schedule of Assessments

The schedule of assessments is shown in [Table 1](#). At each clinic visit, whenever feasible, the cognitive and motor assessments should be prioritized. Study visits should be scheduled at approximately the same time each day to ensure that scales are completed at consistent times during the study.

Table 1 Schedule of Assessments

	Assessment ^a	Visit							
		Screening/ Baseline ^b	Month 6 (±14 d)	Month 12 (±14 d)	Month 18 (±14 d)	Month 24 (±14 d)	Month 30 (±14 d)	Month 36/ ET ^c (±14 d)	Telephone Visit ^d
Study Entrance & Disease History	Informed consent ^d	X							
	Eligibility	X							
	Documentation of CSF1R gene mutation	X							
	Medical/family history and demographics	X							
	Prior/concomitant medications/procedures ^e	X	X	X	X	X	X	X	X
	Urine drug screen	X							
	Urine pregnancy test (WOCBP)	X	X	X	X	X	X	X	
	COVID-19 assessment ^f	Per SOC	Per SOC	Per SOC	Per SOC	Per SOC	Per SOC	Per SOC	
Safety Assessments	C-SSRS ^g	X	X	X	X	X	X	X	X
	Physical and neurological examinations	X	X	X	X	X	X	X	
	Height and weight	X							
	Adverse events ^h	X	X	X	X	X	X	X	X
	Survival assessment ⁱ					X		X	X
	Coagulation for Optional CSF Biomarker Sub-study^j	X		X		X		X	
Biomarkers	Blood sampling (for biomarker analysis)	X	X	X	X	X	X	X ^p	
	Optional CSF Biomarker Sub-study^k	X		X		X		X ^o	
	Magnetic Resonance Imaging (MRI) ^l	X	X	X	X	X	X	X ^q	
Cognitive Assessments	MoCA	X	X	X	X	X	X	X	X
	CDR [®] +NACC-FTLD ^m	X	X	X	X	X	X	X	X
	BAC	X	X	X	X	X	X	X	
	CBFS	X	X	X	X	X	X	X	X
Motor Assessments	2MWT	X	X	X	X	X	X	X	
	TUG	X	X	X	X	X	X	X	
Severity of Illness Scales	CGI-S	X							
	CGI-C		X	X	X	X	X	X	X
	PGI-S	X							
	PGI-C		X	X	X	X	X	X	X
Functional, Psychiatric & Other Assessments	FAQ ⁿ	X	X	X	X	X	X	X	X
	NPI-12 ⁿ	X	X	X	X	X	X	X	X
	Zarit Burden Interview ⁿ	X	X	X	X	X	X	X	X

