4 STUDY DESIGN

4.1 Overall Design

This is a non-interventional, prospective, multicenter, observational, natural history study of patients with ALSP and asymptomatic carriers of *CSF1R* gene mutations, the causative mutation for ALSP. Potential study participants will be screened for study eligibility. Individuals who satisfy the study inclusion and exclusion criteria and who provide written informed consent will be enrolled in the study and followed for up to 36 months.

Clinic visits to assess disease status will be conducted at Screening/Baseline and at Months 6, 12, 18, 24, 30, and 36. Each clinic visit will include clinical assessments (cognitive, motor, functional, psychiatric, severity of illness, and study partner burden assessments) and imaging studies. Blood for biomarker analysis will be collected at Screening/Baseline and at Months 6, 12, 18, 24, 30, and 36. Adverse events (AEs) and concomitant medications and procedures will be recorded throughout the 36-month study.

An optional sub-study to evaluate levels of biomarkers in cerebrospinal fluid (CSF) is also included in this study and will be conducted at select study sites. A CSF sample will be obtained at Screening/Baseline and at Months 12, 24, and 36 from subjects who provide informed consent to participate in the optional CSF Biomarker Sub-study.

Given the nature of ALSP, subjects may progress while on study. If a subject is unable to attend on-site visits due to a decline in his/her condition and the subject is willing to remain in the study, telephone visits may be conducted at Month 18, Month 24, and Month 30 in lieu of clinic visits at the discretion of the Investigator (refer to schedule of assessments, [Table 1](#)) All other visits should occur in clinic. Telephone visits will also require participation of the study partner.

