## **6.2.4 Cognitive Assessments**

### **6.2.4.1 Montreal Cognitive Assessment (MoCA)**

The MoCA is a screening tool that is used to evaluate cognitive abilities and dementia (Nasreddine et al., 2005). The MoCA evaluates different types of cognitive domains, including orientation, short-term memory, delayed recall, abstraction, visuospatial, and executive functioning; language; and attention. Scores range from 0 to 30.

MoCA Tasks and Points:

- Visuospatial/executive score = 5 points
- Naming score = 3 points
- Attention: Digits forward and backward score = 2 points
- Attention: Letter tapping score = 1 point
- Attention: Serial 7 subtraction score = 3 points
- Language: Repeat score = 2 points
- Language: Fluency score = 1 point
- Abstraction score = 2 points
- Delayed recall only score = 5 points
- Orientation score: 6 items (date, month, year, day, place, city) = 6 points

Additionally, the MoCA can be adjusted for education to help account for differences in cognitive abilities due to education.

- Less than or Equal to 12 years of education (1 points if ‘yes’, 0 point if ‘no’)

When all items are complete, the education-adjusted MoCA is a sum of 11 items:

$$MoCA_{Total} = \sum_{i=1}^{11} Tasks_i + Education$$

Where:

- $Tasks_i$  = cognitive domain tasks (point totals from each of  $i$  tasks)
- $Education$  is a dichotomous variable coded as:
  - 1 indicates less than or equal to 12 years of education
  - 0 indicates > 12 years of education
- Education is collected at each study visit, and the education component from each visit will be used (i.e., the baseline education value will not be carried forward to all subsequent visits)
- The maximum possible score is 30, therefore, if a subject scores 30/30, a point is not added if the subject has 12 years of education or less.

If data are missing from one of the tasks, or if education is missing, MoCATotal will be missing. Because the individual item tasks in the MoCA are not collected in the electronic data, and only the point totals are recorded, available item averaging is not an applicable option. If missing data are >20%, a weighted task averaging will be explored in sensitivity analysis.

The MoCA will be completed at Screening/Baseline and at Months 6, 12, 18, 24, 30, and 36/ET.

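### The SAP has no rule for MoCA tests given by telephone, so late-visit MoCA change may be biased by missing or zero-scored tasks in subjects who have declined

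*SAP*

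**What the plan says.** **Telephone visits.** Protocol 4.1 and footnote r of Table 1 say that "telephone visits may be conducted at Month 18, Month 24, and Month 30 in lieu of clinic visits". The condition is that the subject cannot come on site because of decline but is willing to stay in the study. The text continues: "All other visits should occur in clinic. Telephone visits will also require participation of the study partner". Months 6, 12 and 36 are therefore clinic visits.

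**What is done by telephone.** The MoCA row of Protocol Table 1 reads "MoCA X X X X X X X X"; the eighth mark is the Telephone Visit column. The BAC, both walking tests, MRI, blood sampling and physical and neurological examinations have no mark there. The CDR+NACC-FTLD, CBFS, CGI-C and PGI-C do. Protocol 8.3 leaves instructions for the clinical scales to a separate manual.

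**Scoring.** SAP 6.2.4.1 builds the MoCA total from task point totals, including "Visuospatial/executive score = 5 points" and "Naming score = 3 points". The total is missing in this case: "If data are missing from one of the tasks, or if education is missing". The only relief is: "If missing data are >20%, a weighted task averaging will be explored in sensitivity analysis".

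**Recognition in the SAP.** The SAP says that it is based on protocol version 5, but its Table 3 has no telephone column. Section 4.1.10 uses scheduled visits under their nominal label. No variable for visit mode is defined.

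**Use.** SAP 4.3.4 names MoCA change as one of three MMRM models of primary interest, with ventricle volume and CBFS.

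**The concern.** The two documents do not fit together at one point. The protocol keeps the MoCA in the telephone visit after removing most in-person procedures. The SAP then applies an all-or-nothing rule to a score that contains at least one task that looks hard to give by voice. The visuospatial/executive task alone is enough to lose the total.

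The subjects affected are not a random subset, because the entry condition for a telephone visit is decline. Totals lost there are lost for a reason related to the outcome. The CDR sum of boxes, CBFS, FAQ, NPI-12 and Zarit scores all have a prorating rule in the SAP; the MoCA has none in its main derivation.

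Month 36 adds a second route. A subject followed by telephone up to Month 30 who still cannot travel has no permitted Month 36 assessment except the survival call.

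At stake is the late part of the MoCA curve, in a study that is meant to lay the foundation for an external control arm.

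**Working it through.** **1. The plan's own figure.** The ten task scores in SAP 6.2.4.1 sum to 5 + 3 + 2 + 1 + 3 + 2 + 1 + 2 + 5 + 6 = 30, the stated maximum. (The formula there sums 11 tasks and then adds education, but only ten tasks are listed; ten tasks plus education make 11 items.)

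**2. What a telephone visit could lose.**
- Visuospatial/executive only: 5/30 points = 16.7%; 1/10 tasks = 10%. Remaining score: 25 points.
- Naming as well: 8/30 points = 26.7%; 2/10 tasks = 20%. Remaining score: 22 points.

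Either case makes the total missing.

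**3. Does the fallback start?** The trigger is more than 20%, with no base given.
- Counted in points: met if both tasks are lost (26.7%), not met if one is lost (16.7%).
- Counted in tasks: not met in either case, since 20% is not above 20%.
- Counted in MoCA records over the study: not met in the illustration in step 5, where 3% to 13% of records are missing.

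It is met in only one of these readings, and even then it is a sensitivity analysis.

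**4. If tasks not given are entered as 0.** Shift in the visit mean = share on telephone × points falsely lost. The documents give no share, so 10% to 30% is assumed. With up to 8 points lost, the false fall in the mean is at most 0.10 × 8 = 0.8 to 0.30 × 8 = 2.4 points. With 5 points it is at most 0.5 to 1.5.

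**5. If totals are missing.** This is an illustrative simulation; every input below except the sample size is assumed, not taken from the documents.
- One group of 60, baseline MoCA 23 (SD 4), mean slope −2 points a year (SD 1.5 or 2.5), measurement SD 1.5, 100 replicates.
- From Month 18 on, a total is lost when the true score is below a threshold that 10%, 20% or 30% of subjects fall below at Month 36. The Month 36 loss stands for the clinic-only rule.
- Model: visit and baseline × visit with compound symmetry, the SAP's fallback structure. The first-choice heterogeneous structure was not fitted.
- True Month 36 mean change = −2 × 3 = −6.

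| Lost at Month 36 | Slope SD | All subjects | Observed cases | MMRM | MMRM shortfall | Records kept |
|---|---|---|---|---|---|---|
| 10% | 1.5 | −6.02 | −5.39 | −5.58 | 0.44 | 97% |
| 10% | 2.5 | −6.01 | −4.75 | −5.20 | 0.81 | 97% |
| 20% | 1.5 | −6.02 | −4.86 | −5.11 | 0.91 | 93% |
| 20% | 2.5 | −6.01 | −3.79 | −4.44 | 1.57 | 93% |
| 30% | 1.5 | −6.02 | −4.37 | −4.61 | 1.41 | 87% |
| 30% | 2.5 | −6.01 | −2.77 | −3.59 | 2.42 | 87% |

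The MMRM improves on the observed-case mean in every row but does not close the gap. For 20% lost and slope SD 2.5, the shortfall drops from 6.01 − 3.79 = 2.22 to 6.01 − 4.44 = 1.57 points.

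**6. Direction.** Steps 4 and 5 pull in opposite directions and can be of similar size. The SAP does not say which would apply.

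**The case against.** The strongest objection is that the documents do not say how the MoCA is given by telephone. The SAP lists task names and points only, the procedure is in a manual that is not part of these documents, and a study partner must take part. A reader might infer that every telephone visit yields no MoCA total. The documents do not support that: the total is lost only when a task is recorded as missing. This stands, and the point is worded accordingly.

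A reader might also infer that MoCA decline would be estimated mainly from patients still fit to travel. That is not shown. Baseline, Month 6 and Month 12 are clinic visits for everyone, those totals stay in the MMRM, and SAP 4.1.10 maps early termination and unscheduled visits into analysis windows. The illustration keeps 87% to 97% of records.

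Exposure may also be small in the coming analysis. The logs for Amendments 1 to 3 do not mention telephone visits in place of clinic visits, so the option may date from version 5.0 (02 October 2024). That would be about six months before the planned freeze around 11 April 2025. This cannot be confirmed, and follow-up continues to Month 36 in any case.

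Finally, the CBFS, another primary MMRM outcome, consists of questions and is in the telephone column, so decline in homebound subjects is not wholly unseen at Months 18 to 30. The SAP's correlations of primary interest are at Month 12, before any telephone visit. Both points limit the consequence, but neither supplies a MoCA scoring rule.

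**Conclusion.** The gap is real and should be closed. The protocol schedules a MoCA for subjects selected by decline, and the SAP has neither a scoring rule for that setting nor a way to identify it. Its missing-task rule would discard any total that lacks a visual task, and the fallback has no defined base. Month 36 is closed to the same subjects by the visit rule.

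The defensible conclusion is that MoCA change at Months 18 to 36 may be biased by an unknown amount. The shortfall of 0.4 to 2.4 points at Month 36 comes from assumed slopes, loss shares and a single-group model, and shows only that the MMRM need not remove the bias.

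A reader might go further and conclude that natural-history decline is understated and that a later treated cohort would face a control that looks too mild. That follows only if tasks not given are left missing; if they are scored 0, decline is overstated. The number of telephone visits is not given. When any treated comparison is made depends on the Phase 2 documents, which are outside these two.

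**What to change.** **SAP 6.2.4.1.**
- State that a task not administered is missing, never 0.
- Flag visit mode (clinic or telephone) for every MoCA record.
- Define the base of the 20% trigger: points, tasks or records.
- Derive a common-task score at every visit, for all subjects, from the task totals already recorded. It omits the tasks not given by telephone: 30 − 8 = 22 points if both visual tasks are omitted. Treat the education point the same way at all visits, and restate the cap for the shorter score.
- Run the MoCA MMRM on change in this score, telephone visits included, as a supportive analysis beside the full-score model.

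**Protocol 4.1 and Table 1 footnote r.** Extend the existing telephone option, under the same condition, to Month 36/ET for the assessments already in the telephone column.

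**Cost.** Some SAP wording, one extra model on data already collected, and a short protocol change. The common-task score leaves out visuospatial function and does not remove any difference between telephone and clinic testing. A Month 36 telephone visit would have no MRI, blood or motor data, a loss that the protocol already accepts at Months 18 to 30.

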#### **6.2.4.2 Clinical Dementia Rating Scale plus National Alzheimer’s Coordinating Center-Frontotemporal Dementia (CDR®+NACC-FTLD)**

The CDR®+NACC-FTLD is a semi-structured global assessment measure that was developed to measure the severity of dementia symptoms in Alzheimer’s disease and related dementias (Miyagawa et al. 2020).

The 8 domains of the CDR®+NACC-FTLD-SB are:

- Memory (5-point scale ranging from 0-3)
- Orientation (5-point scale ranging from 0-3)
- Judgement and Problem Solving (5-point scale ranging from 0-3)
- Community Affairs (5-point scale ranging from 0-3)
- Home and Hobbies (5-point scale ranging from 0-3)
- Behavior/Comportment/Personality (5-point scale ranging from 0-3)
- Language (5-point scale ranging from 0-3)
- Personal Care (4-point scale ranging from 0-3)

The first 7 domains are rated on a 5-point scale (0 = normal, 0.5 = questionably or minimally impaired, 1 = mildly but definitely impaired, 2 = moderately impaired, and 3 = most severely impaired). The eighth domain, Personal Care, does not have a rating of 0.5 and, therefore, is rated on a 4-point scale.

The total score of CDR®+NACC-FTLD-SB (sum of boxes) is defined as the sum of all 8 domain ratings.

$$\text{CDR®. NACC. FTLD. SB}_{Total} = \sum_{i=1}^8 \text{DomainRating}_i$$

If one or more domains are missing for the sum of boxes calculation, a proportional adjustment will be made, scaling the sum of the observed scores to an equivalent full-score range:

$$\text{CDR®. NACC. FTLD. SB}_{Total\_adj} = \frac{\sum X_i}{N_{Answered}} \times 8$$

Where:

- $X_i$  = 8 domains with item scores ranging from 0-3
- $N_{Answered}$  = number of domain items with a valid response
- 8 = total number of domains in the full CDR®+NACC-FTLD
- Range of the score is 0-24

The Global CDR®+NACC-FTLD uses the same 8 items as the SB (sum of boxes) version. The Global score ranges from 0 to 3 (the lower the better) and is determined using specific scoring rules:

1. If all domains are 0, then the global CDR®+NACC-FTLD score is 0.
2. If the maximum domain score is 0.5, the global CDR®+NACC-FTLD score is 0.5.
3. If the maximum domain score is above 0.5 in any domain, the following applies:
  - a. If the maximum domain score is 1 and all other domains are 0, the global CDR®+NACC-FTLD score is 0.5.
  - b. If the maximum domain score is 2 or 3, and all other domains are 0, the global CDR®+NACC-FTLD score is 1.
  - c. If the maximum score occurs only once, and there is another rating besides 0, the global CDR®+NACC-FTLD score is one level lower than the level corresponding to maximum impairment.
4. If the maximum domain score occurs more than once, then the global CDR®+NACC-FTLD score is the maximum domain score.

The CDR®+NACC-FTLD will be administered by trained site personnel at Screening/Baseline and at Months 6, 12, 18, 24, 30, and 36/ET. At the investigator's discretion, the CDR®+NACC-FTLD may not need to be administered if there are no signs or symptoms of cognitive impairment (i.e., normal score on the MoCA) or if the subject does not have a caregiver who has provided informed consent for this study.

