#### 6.2.4.3.1 CBFS Motor Experiences of Daily Living (CBFS-M)

The CBFS-M Assesses how motor symptoms impact daily activities. The CBFS-M is calculated by summing (adding) the scores from 14 items.

If all 14 items are answered, the formula for the CBFS-M is a simple sum:

$$CBFSm_{Total} = \sum_{i=1}^{14} X_i$$

If only one (<10% of data) of 14 motor EDLs is missing, the available item mean multiplied by 14 will be used.

$$CBFSm_{Total\_Adj} = \left( \frac{\sum X_i}{N_{Answered}} \right) \times 14$$

Where:

- $X_i$  = individual motor-related item scores (from 0 to 4)
- $N_{Answered}$  = number of motor-related items with a valid response
- 14 = total number of items in the full CBFS-M score
- Range of the score is 0 to 56

If 2 or more of the 14 items are missing, the total CBFS-M score will be set to missing.

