### 6.2.7.3 Zarit Burden Interview (ZBI)

The ZBI is a 22-item self-report questionnaire designed to evaluate the impact of caregiving on the primary caregiver (Zarit, Reever & Bach-Peterson, 1980). It assesses caregiver burden across 22 different domains, measuring physical, emotional, and social strain.

Each item on the interview is a statement that the caregiver is asked to rate using a 5-point scale that ranges from 0 (“never”) to 4 (“nearly always”). The first 21 items are scored: 0-never, 1-rarely, 2-sometimes, 3-quite frequently, and 4-nearly always. The final item, “Overall, how burdened do you feel in caring for your relative?” is scored on a comparable 5-point scale: 0-not at all, 1-a little, 2-moderately, 3-quite a bit, and 4-extremely. A total score is computed by summing together the 22 items.

The ZBI will be completed at Screening/Baseline and at Months 6, 12, 18, 24, 30 and 36/ET.

A ZBI total score is calculated by summing (adding) the scores of the 22 item scores together.

If all 22 items are answered, the formula for the ZBI total is a simple sum:

$$ZBI_{Total} = \sum_{i=1}^{22} X_i$$

If only one or two (<10%) ZBI questionnaire items are missing, the available item mean multiplied by 22 will be used:

$$ZBI_{Total\_Adj} = \left( \frac{\sum X_i}{N_{Answered}} \right) \times 22$$

Where:

- $X_i$  = individual item scores (from 0 to 4)
- $N_{Answered}$  = number of items with a valid response
- 22 = total number of items in the full ZBI scale
- Range of the score is 0 to 88

If 3 or more of the 22 items on the scale are missing, the total ZBI scores ( $ZBI_{Total}$  and  $ZBI_{Total\_ADJ}$ ) will be set to missing. To reduce bias due to missing data,  $ZBI_{Total\_ADJ}$  will serve as the primary variable for reporting on the ZBI, and  $ZBI_{Total}$  will be included in the ADaM datasets for future sensitivity analyses beyond the scope of this SAP.

The foundational study introducing the ZBI (Zarit, Reever & Bach-Peterson, 1980) identified the basic scoring principles but did not explicitly detail handle missing items. Little & Rubin (2002) support the approach of using the mean of completed items in psychological scales when a small proportion of the times are missing.

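### The CDR+NACC-FTLD Sum of Boxes is pro-rated with no minimum number of rated domains, although the SAP's other multi-item scales each have a cut-off beyond which the score is missing

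*SAP*

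**What the plan says.** SAP 6.2.4.2 states that the Sum of Boxes "is defined as the sum of all 8 domain ratings". Seven domains take the values 0, 0.5, 1, 2 or 3. The eighth, Personal Care, "does not have a rating of 0.5 and, therefore, is rated on a 4-point scale".

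For incomplete forms the rule is: "If one or more domains are missing for the sum of boxes calculation, a proportional adjustment will be made". The aim is to bring a partial total onto the range of a complete form. The divisor is the "number of domain items with a valid response", and the multiplier is 8. The section adds: "Range of the score is 0-24". It gives no lower limit on the number of domains rated and no condition under which the score becomes missing. SAP 4.1.11 refers scale-specific rules to the Appendix and sets no overriding threshold. Protocol 8.3.1.2 defines the Sum of Boxes as a total over 8 domains and has no rule for missing ones.

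The neighbouring scales are handled differently. For CBFS-M (SAP 6.2.4.3.1): "If 2 or more of the 14 items are missing, the total CBFS-M score will be set to missing". For the Zarit interview (SAP 6.2.7.3) the total is lost "If 3 or more of the 22 items on the scale are missing". CBFS-NM, FAQ, NPI-12 Total and NPI-12 Distress also have cut-offs, and the MoCA total is missing if any single task is missing.

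**The concern.** Scaling up from the mean of the rated domains treats the missing domains as if they resembled the rated ones. With one domain missing, that assumption carries little weight. With six or seven missing, it supplies most of the score. SAP 6.2.7.3 itself defends the item-mean approach only where a small share of items is missing.

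The domains are also not interchangeable. Protocol 8.3.1.2 says the scale was chosen because frontal involvement and behavioral symptoms are common in ALSP, so uneven profiles are to be expected. A change from baseline that compares a complete form with one extrapolated from one or two domains could then reflect which domains were rated rather than progression.

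The Sum of Boxes is a baseline characteristic (SAP 4.2.2), a change-from-baseline endpoint (SAP 4.3.2.1) and one of the clinical endpoints in the correlations (SAP 4.4). In a study of about 60 subjects, a few such values could matter.

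**Working it through.** **Inputs (SAP 6.2.4.2).** There are 8 domains. Ratings are 0, 0.5, 1, 2 or 3, or 0, 1, 2 or 3 for Personal Care. Score = (sum of observed ratings / N) x 8, where N is the number of domains rated.

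**The plan's own figure.** A complete form runs from 8 x 0 = 0 to 8 x 3 = 24, which reproduces the stated range.

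**One domain rated.** Score = rating / 1 x 8. For a five-level domain this gives 0, 4, 8, 16 or 24; for Personal Care, 0, 8, 16 or 24. The share of the scale missing is 7/8 = 87.5%.

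**Worst-case gap.** Let S be the sum of the N rated domains and M the unseen sum of the other 8 - N.

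- Pro-rated minus true = 8S/N - (S + M) = S(8 - N)/N - M.
- S lies between 0 and 3N, and M between 0 and 3(8 - N).
- The extremes are S = 3N with M = 0, and S = 0 with M = 3(8 - N). Both give an absolute gap of 3 x (8 - N).

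| Domains rated | Missing | Worst-case gap (points) |
|---|---|---|
| 7 | 12.5% | 3 |
| 6 | 25% | 6 |
| 5 | 37.5% | 9 |
| 4 | 50% | 12 |
| 3 | 62.5% | 15 |
| 2 | 75% | 18 |
| 1 | 87.5% | 21 |

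**A less extreme illustration (assumed profile, not study data).** Behavior is 2; Memory, Judgement, Community Affairs, Home and Hobbies, and Language are 0.5 each; Orientation and Personal Care are 0. The true sum is 2 + 5 x 0.5 = 4.5.

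- Only Behavior rated: 16. Only Memory rated: 4. Only Orientation rated: 0.
- A complete baseline of 4.5 followed by a Behavior-only form with no true change: 16 - 4.5 = +11.5.
- Seven rated, Behavior missing: 2.5/7 x 8 = 2.86. Seven rated, Personal Care or Orientation missing: 4.5/7 x 8 = 5.14. Seven rated, one of the 0.5 domains missing: 4/7 x 8 = 4.57.

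With one domain missing, this profile is off by at most 4.5 - 2.86 = 1.64 points.

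**What the other scales tolerate before the score is missing.**

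| Scale | Most that may be missing |
|---|---|
| MoCA | none |
| CBFS-M | 1/14 = 7.1% |
| CBFS-NM | 1/17 = 5.9% |
| FAQ | 1/10 = 10% |
| NPI-12 Distress | 1/12 = 8.3% |
| NPI-12 Total | one frequency and/or one severity item |
| Zarit | 2/22 = 9.1% |
| CDR Sum of Boxes | 7/8 = 87.5% |

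NPI-12 Total is not a clean precedent. If the missing frequency item and the missing severity item fall in different domains, 2 of 12 products (16.7%) are lost, and the section's next rule can be read as excluding that case. It still has a cut-off. The CBFS total is the sum of two components that each have one.

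**The case against.** The strongest reply is that the harm is hypothetical. The missing data that the documents describe for this scale concern the whole form: the investigator may omit it when the MoCA is normal or no caregiver has consented. A wholly omitted form has N = 0, the formula is undefined, and no score arises. Trained site personnel administer the scale, and neither document gives a rate of partial completion. All of this stands. Partial forms remain possible, for example at the telephone visits for declining subjects, where protocol Table 1 schedules the scale, but their number is unknown.

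A second reply is that the score carries limited weight. This also stands. The primary models in SAP 4.3.4 cover ventricle volume, MoCA and CBFS; the correlations of primary interest in SAP 4.4 pair ventricle volume with MoCA and CBFS; and SAP 4.1.6 calls the study exploratory. The protocol's endpoint list names the CDR+NACC-FTLD without specifying the Sum of Boxes; it is SAP 4.3.2.1 that does so.

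A third reply is that the adjusted total has its own name and that SAP 4.1.12 provides outlier flagging, plausibility review and source checks. These are partial safeguards. The three-standard-deviation flag applies only to selected variables, an extrapolated value always lies within 0-24, and values judged valid but extreme stay in the primary analysis.

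Two stronger readings are tempting. A reader might infer that study results will be materially distorted; without a rate of partial forms the documents do not support that. A reader might also infer that the SAP applies one 10% rule from which this scale departs; it does not, as MoCA and NPI-12 Total show.

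**Conclusion.** The point holds as a defect in a stated scoring rule. Nothing else in either document supplies a minimum number of rated domains. Followed literally, the rule turns one rated domain into a reportable score of up to 24, with a possible error of 21 points. No reason is given for treating this scale differently from the others.

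The error sizes are bounds set by the formula, not expected errors. The conclusion assumes that the adjusted total is the value reported: the section says the adjustment will be made, but unlike FAQ, NPI-12 and Zarit it does not name the reporting variable. The exposure is confined to partly completed forms, and to the descriptive change-from-baseline summaries, the baseline table and the correlations outside those of primary interest. This is a correction worth making because it is cheap, not a threat to the main analyses.

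**What to change.** Replace the rule in SAP 6.2.4.2 with: *If exactly 1 of the 8 domains is missing, the sum of the observed ratings is divided by 7 and multiplied by 8; if 2 or more are missing, the Sum of Boxes is set to missing.* State in the same place that this value is the reporting variable.

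The cut-off is a proposal. It matches the one-item allowance for CBFS-M, CBFS-NM, FAQ and NPI-12 Distress and brings the worst-case gap down from 21 points to 3. One domain of 8 is 12.5%, so a strict 10% limit would permit no pro-rating at all; that would also close the gap, at the price of more missing scores.

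The section has no missing-domain rule for the Global score either. If one is added, it should be programmable: *the Global score is set to missing if any of the 8 domains is missing.* This discards some incomplete forms whose Global score is already determined, such as two domains rated 3, which give 3 whatever the rest would have been.

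The cost is one or two SAP sentences and the loss of some partial ratings. How many cannot be told from the documents; a count of forms by number of domains rated would show it.
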